7.1. Intervention

The trial intervention is a standardised diagnostic assessment (SDA) tool, the Development and Well-Being Assessment (DAWBA).[18] The DAWBA consists of a structured package of questionnaires based on diagnostic criteria, which generate computer algorithm-derived diagnostic predictions.[18]

The DAWBA has been widely used, as both a screening and diagnostic tool and outcome measure in previous research in both clinical and community settings [19, 20], in other trials of SDAs[16, 17] and in large scale epidemiological research.[21-23] The DAWBA has been used as an assessment tool within CAMHS for conditions such as hyperkinetic disorder as well as being used outside the UK.[24, 25] The DAWBA has established reliability and validity.[15]

The DAWBA will be completed by:

- The parent/carer of children/young people aged <16
- Children/young people aged 11-15, if participating
- Young people aged 16 and 17
- The parent/carer of young people aged 16 and 17, if participating with the young person

A summary report of the DAWBA results will be sent to participants and CAMHS clinicians, as an adjunct to usual clinical practice (review of the CAMHS referral as usual).

7.2. Comparator

The comparator will be usual clinical practice (review of the CAMHS referral as usual) that does not include the use of SDA tools at the point of referral receipt.

Information from SDA tools do not normally accompany referrals to CAMHS nor are they used at the point of referral receipt (i.e., this is not usual practice and is therefore very unlikely to change during the course of the trial).

7.3. Intervention Delivery

7.3.1. Intervention Access

For the intervention group, the DAWBA will be completed on a secure online platform.[18] Access will be via a unique ID number and password, which will be assigned at the point of randomisation. The unique ID number and password will be provided following completion of baseline data collection. The details will be presented on screen within the online data collection system and additionally will be sent to participants by text and / or email.

If possible (i.e., where permission was granted to collect contact details for all respondents) each DAWBA respondent will be sent their own login details. If this is not possible, the details for all DAWBA respondents will be sent to the primary participant (i.e., the parent/carer for young people aged <16 or the young person themselves if aged 16 or 17 years), and the primary participant will be asked to pass on the relevant DAWBA access details to other respondents.

Participants will also be able to complete the DAWBA in a telephone call with the STADIA researcher if required. In this case, the researcher will access the DAWBA slot for the participant via the unique ID number and password and will record the respondent's responses directly into the online system.

Trial name:	STADIA	Protocol version:	4.1	Date:	01-Aug-2022	Page:	32 of 73
Written using WPD							

7.3.2. Accountability Procedures

The required number of unique DAWBA 'slots' will be pre-loaded into the online randomisation system and a stock control system will assign slots at the point of randomisation to those participants who are allocated to the intervention group.

The DAWBA is hosted on a standalone online system, provided, hosted and maintained by the DAWBA developer.[18]

The online DAWBA system enables oversight of access and completion to monitor uptake of the intervention. DAWBA completion will be monitored and participants who have not completed the assessment within 2-3 days of randomisation will be contacted by the researcher to support and encourage online completion, or offer telephone completion if required. Wherever possible, the DAWBA should be completed, and the report prepared and sent to the participant(s) and CAMHS clinician, within 10 working days of receipt of the CAMHS referral although up to an additional 3 working days may be offered for DAWBA completion for those participants randomised close to the 10 working day deadline. For sites where the waiting time for the CAMHS acceptance decision usually exceeds 10 working days, additional time for DAWBA completion and report provision may be offered, providing the DAWBA report is available prior to the CAMHS referral decision. DAWBA reports should be generated as soon as practicably possible following DAWBA completion.

All DAWBA records will be locked before generation of the DAWBA report. Participants will be encouraged to use the functionality within the DAWBA system to confirm when they have finished entering data. When this has been indicated, the DAWBA record will be manually locked by trial staff and the DAWBA report will be generated.

If the DAWBA has been fully answered but has not been confirmed as complete by the participant, the STADIA researcher will aim to liaise with the participant to confirm whether they have finished entering data and, if so, the DAWBA record will be manually locked by trial staff and the DAWBA report will be generated.

If the DAWBA report has not been fully answered and has not been confirmed complete by the participant, the STADIA researcher will aim to liaise with the participant to encourage and support completion wherever possible. If the participant confirms that they do not wish to continue completion of the DAWBA, the DAWBA record will be manually locked by trial staff and the DAWBA report will be generated on the basis of the partial responses provided.

If the participant cannot be contacted to confirm completion, the DAWBA record will be manually locked by trial staff and the DAWBA report will be generated on the basis of the responses entered after 10-13 working days from receipt of the CAMHS referral or identification of potential participant.

7.3.3. Intervention Modification

The DAWBA is a modular assessment and only selected modules relevant to emotional difficulties and comorbid disorders will be included.

The DAWBA includes automatic skip rules based on screening questions to maximise relevance to individual participants.

Trial name:	STADIA	Protocol version:	4.1	Date:	01-Aug-2022	Page:	33 of 73	
Written using WPD	Written using WPD 3.1 version 2.0 30-Oct-2017. Effective date: 30-Nov-2017. Template Author: [name]							

Participants will be asked to complete all sections of the DAWBA presented to them. Should the DAWBA be only partially completed by respondents at the time the DAWBA report is generated the report will be based only on fully answered sections with missing responses identified as such.

Following DAWBA completion, a trial specific DAWBA report will be prepared for each participant, based on a standard template. The computer algorithm-derived DAWBA diagnostic predictions will be used to highlight the probability of a child/young person meeting criteria for an emotional disorder or common comorbid disorders.

We will feedback the results of the DAWBA by making the DAWBA report available to:

- 1. CAMHS practitioners the triage team making the decision about the referrals and, if accepted, subsequent assessing / treating clinicians. The DAWBA will also be added to the CAMHS record.
- 2. The parent/carer and young person the primary participant (i.e., the parent/carer of children/young people aged <16 or the young person aged 16 and 17) will be sent a copy of the DAWBA report and will also be encouraged to take this along to each CAMHS appointment so that any clinician that they might see is aware of it. The parent/carer of the young person aged 16-17, if they are participating, will also receive a copy of the DAWBA report via the primary participant.

8. Trial procedures and assessments

8.1. Summary of assessments

The summary of assessment is detailed in Table 5.

Trial name:	STADIA	Protocol version:	4.1	Date:	01-Aug-2022	Page:	34 of 73
Written using WPD	Written using WPD 3.1 version 2.0 30-Oct-2017. Effective date: 30-Nov-2017. Template Author: [name]						

Table 5. Summary of assessments

Time-point	Maxim	um 10 working	days from ref	6 months post- randomisation	12 months post- randomisation	18 months post- randomisation		
Activity	Screening and invitation	Eligibility and enrolment	Consent and baseline			Follo	w-Up	
Initial eligibility screen of referral information	Х							
Telephone invitation to participate	Х							
Verbal agreement to participate		X						
Confirm eligibility		X						
Obtain enrolment data		X						
Participant enrolment		Х						
Written informed consent/assent (online)			Х		Intervention			
Baseline demographics (parent/carer and young person aged 16 & 17)			Х		DAWBA in			
MFQ (parent/carer and child/young person aged 11+)			х	sation	addition to usual	Х	Х	
RCADS (parent/carer and child/young person aged 11+)			х	Randomisation	practice	Х	Х	
SDQ (parent/carer and child/young person aged 11+)**			Х	Ran	Or	х	Х	
Self-harm measure (child/young person aged 11+ only)			Х		Usual practice only	х	х	
PHQ-9 (parent/carer only)			Х	-		Х	Х	
GAD-7 (parent/carer only)			х	-		Х	Х	
CHU9D (child/young person self-report if aged 11+ or parent/carer proxy if child aged <11 or 11-			х			x	Х	
15 and not self-reporting)								
EQ5DY (child/young person self-report if aged 11+ or parent/carer proxy if child aged <11 or 11- 15 and not self-reporting)			х			x	х	
EQ5D5L (parent/carer only)			Х	1		Х	Х	
Trial name: STADIA Protocol version: 4.1	Date: 01-A	ug-2022 Pa	ge: 35 of 7	3	1	1		1

Resource Use Questionnaire (parent/carer and young person aged 16 & 17)		x		х	х	
CRIES-8 (child/young person self-report if aged						
11+ or parent/carer proxy if child aged <11 or 11-		X		X	Х	
15 and not self-reporting)						
Data collection from records***		X		Х	Х	Х
* For sites where the waiting time for the CAMHS accepta	nce decision usuall	y exceeds 10 workir	ng days from refe	rral receipt, recruitme	nt activities may	
start and/or continue beyond 10 working days from refer	ral receipt, providin	g the intervention p	period can be con	pleted prior to the CA	MHS referral	
decision.						
**For participants in the intervention arm, the baseline S	DQ will be collected	l as part of the DAW	/BA, completed p	ost-randomisation.		
***Data collection from records will be completed period	ically throughout th	ne 18 month follow-	-up period.			

Trial name:STADIAProtocol version:4.1Date:01-Aug-2022Page:36 of 73	Trial name: STADIA	Protocol version: 4.1	Date:	01-Aug-2022	Page:	36 of 73
--	--------------------	-----------------------	-------	-------------	-------	----------

8.2. Schedule of Assessments

8.2.1. Invitation and screening

Initial eligibility to approach is confirmed by a review of CAMHS referral information and eligible participants are invited to consider participation. Basic screening information obtained from the CAMHS referral is recorded on the Screening and Enrolment Log, including the child/young person's age and sex.

8.2.2. Eligibility and enrolment

If the participant agrees, enrolment information and contact details are obtained from the participant and the participant is enrolled on the trial database.

8.2.3. Consent and baseline

Informed consent is provided using the online eICF, following which, the following baseline demographic data is obtained from participants:

- Gender (of child/young person and parent/carer)
- Ethnicity (of child/young person and parent/carer)
- Age (of child/young person and parent/carer)
- Parent/carer relationship to child/young person
- Education/employment status including type of school if in education (of child/young person)
- Deprivation index (derived from postcode of child/young person's primary residence)

The following baseline participant questionnaires will be completed online:

- Mood and Feelings Questionnaire (MFQ)
- Revised Children's Anxiety Depression Scale (RCADS)
- Strengths and Difficulties Questionnaire (SDQ); included in baseline questionnaires for control arm participants only, extracted from DAWBA for those in the intervention arm
- Child/young person self-report self-harm measure
- Patient Health Questionnaire (PHQ-9)
- Generalised Anxiety Disorder (GAD-7)
- Child Health Utility Instrument (CHU9D)
- EuroQol Quality of Life Questionnaire 5 Domains for Young People (EQ5DY)
- EuroQol Quality of Life Questionnaire 5 Domains, 5 Levels (EQ5D5L)
- Resource Use Questionnaire
- Child Revised Impact of Events Scale (CRIES-8)

In addition the following data is obtained from CAMHS records:

- Child/young person's date of birth
- Details of current and any previous CAMHS referrals
- Previous or existing diagnoses

8.2.4. Randomisation

Following randomisation, the DAWBA will be completed by participants in the intervention arm and the DAWBA report generated and sent to the participant and CAMHS clinicians.

Trial name:	STADIA	Protocol version:	4.1	Date:	01-Aug-2022	Page:	37 of 73
Written using WPD	Written using WPD 3.1 version 2.0 30-Oct-2017. Effective date: 30-Nov-2017. Template Author: [name]						

8.2.5. Follow-up data collection from participants

6 months post-randomisation

The following participant-reported data collection will be completed online*:

- MFQ
- RCADS
- SDQ
- Child/young person self-report self-harm measure
- PHQ-9
- GAD-7
- CHU9D
- EQ5DY
- EQ5D5L
- Resource Use Questionnaire
- Participant self-report diagnoses
- CRIES-8

12 months post-randomisation

The following participant-reported data collection will be completed online*:

- MFQ
- RCADS
- SDQ
- Child/young person self-report self-harm measure
- PHQ-9
- GAD-7
- CHU9D
- EQ5DY
- EQ5D5L
- Resource Use Questionnaire
- Participant self-report diagnoses
- CRIES-8

* Whilst baseline and follow-up questionnaires are intended to be completed online by participants in the first instance, there will be the option for telephone completion, should participants have difficulty accessing or completing the questionnaires online.

8.2.6. Follow-up data collection from records

The following data will be collected from CAMHS records for the 18 month period from randomisation. Periodic searches will be completed over the 18 month reporting period.

- CAMHS referrals and outcome including re-referral
- Documented diagnoses*
- Treatments offered and given
- Deaths

	Trial name:	STADIA	Protocol version:	4.1	Date:	01-Aug-2022	Page:	38 of 73
1	Written using WPD 3.1 version 2.0 30-Oct-2017. Effective date: 30-Nov-2017. Template Author: [name]							

*Site researchers will be allowed to review appointment outcome letters that have been sent up to 3-months after the 12-month and 18-month cut-off, to ascertain information relating to a clinician-made diagnosis decision about the presence of an emotional disorder. The letter must specifically reference the appointment/contact where the appointment/contact is within the 12- or 18-month timeframe. The lag between clinic appointments and appointment outcome letters is variable between Trusts and in some instances can take up to 3 months for the letter to be produced, sent to the patient/GP and uploaded to the clinical records.

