Trial name:	STADIA	Protocol version:	4.1	Date:	01-Aug-2022	Page:	48 of 73
Multime and MUDD	2.4		1-1- 20 NI- 20	M 7 T	L. A. Iban [name]		

Outcome	Measurement	Definition	Analysis metric	Data collection	Time point
Confirmed diagnosis decision	Diagnosis of an emotional disorder or confirmed absence of an emotional disorder coded as 'yes' vs. uncertainty about the presence of an emotional disorder coded as 'no'	Diagnosis as defined above for primary outcome.	Risk ratio/risk difference	Collected from clinical records	Within a) 12 months and b) 18 months of randomisation
Time from randomisat ion to diagnosis of emotional disorder	The time (in days) from randomisation to diagnosis will be derived from the randomisation date and date of diagnosis.	Date of diagnosis will be the first documented eligible diagnosis. Diagnosis as defined above for primary outcome.	Time to event	Collected from clinical records	Within a) 12 months and b) 18 months of randomisation
Diagnoses made	Pre-specified diagnoses will be captured using a standard proforma. Alternative possible diagnoses identified from the clinical notes will be recorded verbatim on the data capture form and will be subject to adjudication by	The diagnosis must be documented in the clinical record within 12 and 18 months of randomisation by a mental health services clinician in an NHS-delivered or NHS-commissioned service. All diagnoses made within 12 and 18 months will be included.	Descriptive There will be separate reporting for: 1. Diagnoses of emotional disorders 2. Alternative / cormobid clinical diagnoses	Collected from clinical records	Within a) 12 months and b) 18 months of randomisation

Trial name:STADIAProtocol version:4.1Date:01-Aug-2022Page:49 of 73	Trial name: STADIA	Protocol version: 4.1	Date:	01-Aug-2022	Page:	49 of 73
--	--------------------	-----------------------	-------	-------------	-------	----------

Outcome	Measurement	Definition	Analysis metric	Data collection	Time point
	members of the Trial				
	Management Group.				
Treatment offered for diagnosed emotional disorder	There is a documented diagnosis of an emotional disorder AND a documented treatment plan = yes No documented diagnosis of emotional disorder and / or no documented treatments offered = no	Whether treatment was offered for a diagnosed emotional disorder, as defined for primary outcome above.	Risk ratio/risk difference	Collected from clinical records	Within a) 12 months and b) 18 months of randomisation

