Treatments / interventio ns given	Pre-specified treatments will be captured using a standard proforma. Alternative possible treatments identified from the clinical notes will be recorded verbatim on the data capture form and will be subject to adjudication by members of the Trial Management Group.	All treatments/interventions offered by CAMHS for any reason within 12 and 18 months of randomisation, whether or not there is a documented diagnosis will be included.	Descriptive There will be separate reporting for: 1. Treatments offered for emotional difficulties 2. Treatments offered for other difficulties	Collected from clinical records	Within a) 12 months and b) 18 months of randomisation

	Trial name: STADIA	Protocol version: 4.1	Date:	01-Aug-2022	Page:	50 of 73
--	--------------------	-----------------------	-------	-------------	-------	----------

Outcome	Measurement	Definition	Analysis metric	Data collection	Time point
Time from	The time (in days)	Date of decision will be the first date that the decision	Time to event	Collected from	Within a) 12
randomisat	from randomisation to	to offer treatment for a diagnosed emotional disorder is		clinical records	months and b)
ion to the	the date of the	documented in the clinical notes.			18 months of
decision to	decision to offer				randomisation
offer	treatment for a				
treatment	diagnosed emotional				
for a	disorder will be				
diagnosed	derived from the				
emotional	randomisation date				
disorder	and the date of the				
	documented decision.				
Time from	The time (in days)	Date of treatment will be the first date that any	Time to event	Collected from	Within a) 12
randomisat	from randomisation to	treatment offered for a diagnosed emotional disorder is		clinical records	months and b)
ion to start	start of first treatment	started.			18 months of
of first	for a diagnosed				randomisation
treatment	emotional disorder	Treatment and diagnosed emotional disorder as			
for a	will be derived from	defined as above.			
diagnosed	the randomisation				
emotional	date and documented				
disorder	start date of first				
	relevant treatment.				
Time from	The time (in days)	Date of decision will be the first date that the decision	Time to event	Collected from	Within a) 12
randomisat	from randomisation to	to offer any treatment is documented in the clinical		clinical records	months and b)
ion to the	the date of the	notes.			18 months of
decision to	decision to offer any				randomisation
offer any	treatment will be				

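### The three-month allowance for late appointment letters covers the diagnosis but not the treatment plan in the same letter, so the treatment-offered outcome can be understated, certainly at the 18-month cut-off.

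*Protocol*

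**What the plan says.** Protocol Section 8.2.6 lists what is taken from CAMHS records for the 18 months from randomisation, using periodic searches. The list includes "Documented diagnoses", which carries an asterisk, and "Treatments offered and given", which does not. The asterisked note reads: "Site researchers will be allowed to review appointment outcome letters that have been sent up to 3-months after the 12-month and 18-month cut-off", and gives the purpose as "to ascertain information relating to a clinician-made diagnosis decision about the presence of an emotional disorder". The letter must refer to an appointment or contact inside the 12- or 18-month window. The stated reason is that the lag is not the same in every Trust: "in some instances can take up to 3 months for the letter to be produced, sent to the patient/GP and uploaded to the clinical records".

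Table 6 in Section 13.1 then sets these rules:

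- **Treatment offered for a diagnosed disorder.** This is scored yes when there is a documented diagnosis "AND a documented treatment plan = yes". The time points are 12 and 18 months, and the analysis is a risk ratio and risk difference.
- **Time to the decision to offer treatment** (for a diagnosed disorder, and for any treatment). "Date of decision will be the first date that the decision" appears in the clinical notes. These are time-to-event outcomes.
- **Time to diagnosis.** The date is that of the first eligible diagnosis to be documented.
- **The diagnosis outcomes, including the primary.** The diagnosis has to be in the clinical record within 12 months (or 18 for the later outcome). The row does not mention the late-letter allowance.

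**The concern.** The treatment-offered outcome has two components that often arise at one appointment and may be recorded in one letter. The protocol gives the diagnosis three extra months to reach the record and gives the plan none. The reason for the allowance, slow letters, applies equally to both. A child seen just before a cut-off could then be coded as diagnosed but not offered treatment only because the letter was slow.

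This matters because the outcome is formally compared between arms, and because diagnosis leading to treatment is part of the trial's first objective (Section 2.1). If part of the proportion offered treatment reflects letter turnaround at each Trust, it measures administration as well as care.

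A second, separate matter is dating. Where an event takes its date from documentation, the time-to-event outcomes carry the same Trust-specific lag throughout follow-up, not only at the cut-offs.

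**Working it through.** **The plan's own figures.** The protocol gives no figure for letter lag (beyond the three-month maximum), for the share of diagnosed children offered treatment, or for the treatment-offered outcome. The nearest figures are the diagnosis rates in Section 13.2.6: 45% in control and 55% in the intervention arm, with 544 per arm. The 544 reproduces with a continuity correction (524 without it), and 544 / 0.90 = 604.4, rounded up to 605. The sample size is not in dispute. The rates are used below only as stand-ins.

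**Step 1: the rules at each cut-off.** Take an in-window appointment at which a diagnosis and a plan are both made, recorded only in a letter sent after the cut-off.

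- *18 months (visit at 17.5, letter at 19).* The footnote admits the letter for the diagnosis. Record collection covers 18 months, and nothing else in the protocol admits a later document for treatment. The result is diagnosis yes, treatment offered no.
- *12 months (visit at 11.5, letter at 13.5).* The letter falls within routine collection, which runs to month 18. The treatment row states a time point but no explicit documentation deadline. If the window refers to when the offer was made, the plan counts. If it refers to when the plan was documented, it does not. The text allows either reading.

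The error runs one way: an offer can be missed, but none can be created.

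**Step 2: size under stated assumptions.** Assume diagnosing appointments are spread evenly over T months and the plan is made at that visit. Let u be the share of plans recorded only in the letter. Then

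share of offers lost = u × mean lag / T.

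With u = 1:

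| Mean lag (months) | 12-month cut-off, documentation reading | 18-month cut-off |
|---|---|---|
| 0.5 | 0.5/12 = 4.2% | 0.5/18 = 2.8% |
| 1.0 | 1.0/12 = 8.3% | 1.0/18 = 5.6% |
| 1.5 | 1.5/12 = 12.5% | 1.5/18 = 8.3% |

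The ceiling, with every letter three months late, is 3/12 = 25% and 3/18 = 16.7%. The protocol says that three months is reached only sometimes. If 10% to 25% of letters took three months and the rest had no lag, the loss would be 0.10 × 3/12 = 2.5% to 0.25 × 3/12 = 6.25% at 12 months, and 1.7% to 4.2% at 18 months. If half of plans were also in same-day notes (u = 0.5), every figure would halve.

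**Step 3: effect on the arm comparison.** For illustration, suppose all diagnosed children are offered treatment (45% and 55%), letter lag is uniform over 0 to 3 months, and the 12-month documentation reading applies. Half of the offers made in the last three months are then lost, so recorded rate = true rate × (1 − s/2), where s is the share of that arm's diagnoses falling in those months. Fix s = 25% in control: 45 × 0.875 = 39.4%.

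| s, intervention arm | Recorded rate | Difference (true 10.0) | Ratio (true 1.22) |
|---|---|---|---|
| 25% | 55 × 0.875 = 48.1% | 8.75 points | 1.22 |
| 20.5% | 55 × 0.8975 = 49.4% | 10.0 points | 1.25 |
| 15% | 55 × 0.925 = 50.9% | 11.5 points | 1.29 |

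Equal timing shrinks the difference and leaves the ratio alone. Earlier diagnosis in the intervention arm raises the ratio, and raises the difference once s falls below about 20.5%. The protocol gives no value for s in either arm.

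**Step 4: dating.** For the visit at 11.5 with its letter at 13.5, Table 6 would date the decision to offer treatment at 13.5 if the letter is its first record. Time to diagnosis also runs to first documentation, and the footnote does not say how a diagnosis from a late letter is dated. Time to start of treatment uses the recorded start date, so a decision can be dated after the treatment it led to. Read literally, the primary-outcome row also rejects a diagnosis first documented at 13.5, which Section 8.2.6 accepts.

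**The case against.** Three stronger readings are tempting, and the protocol does not support them.

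- *A child must be coded diagnosed but not offered treatment at 12 months.* The treatment row sets no explicit documentation deadline and records are searched to month 18, so the plan can be found and assigned to the earlier appointment. This objection stands. The result at 12 months is one reading, whereas at 18 months it follows from the text.
- *The narrow allowance delays the decision date.* It does not. The delay comes from Table 6 dating by documentation, which affects every lagged letter during follow-up. Extending the allowance alone would not change it.
- *The trial is biased towards the intervention.* Section 1.1 says only that more timely conclusions to assessment might logically be expected, and gives no timing figures. With equal timing in the two arms the risk difference shrinks.

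Three further points carry some weight. Many plans may be in same-day notes, which reduces the loss. Only secondary outcomes are affected by the treatment gap, and Section 13.2.1 treats these as supportive. Data collection guidelines are documented separately (Section 8.3) and may contain abstraction detail. They could not, however, quietly widen a limit that the protocol states in terms.

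**Conclusion.** The gap is real but modest. The late-letter allowance is written for diagnosis only, while the treatment-offered outcome needs a plan as well. At 18 months, and at 12 months on the documentation reading, this can only understate the proportion offered treatment. The protocol does not give the lag distribution, the share of plans recorded only in letters or the timing of diagnoses, so the size cannot be computed. On the even-spread, letter-only assumptions it is 2.8% to 8.3% of offers at 18 months for mean lags of 0.5 to 1.5 months, and smaller where notes are made on the day. Its effect on the contrast between arms could go either way.

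The dating rule is a separate weakness with its own cause. So is the conflict over the diagnosis itself: Section 8.2.6 accepts later letters while Table 6 requires documentation inside the window. That conflict reaches the primary outcome's definition.

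**What to change.** Two changes are needed, because there are two causes.

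1. In Section 8.2.6, extend the late-letter note to the treatment item on the existing condition: the letter must refer to an appointment or contact within the 12- or 18-month window.
2. Reconcile Section 8.2.6 with the Table 6 rows for the diagnosis outcomes, time to diagnosis, treatment offered and the two decision-to-offer times. State once that the appointment or contact date governs both whether an event falls in the window and how it is dated, for diagnosis and for the decision to offer treatment alike. Use the documentation date only where no appointment date is given. Changing the treatment rows alone would leave time to diagnosis on the documentation date, so that a child could have a treatment decision dated before the diagnosis it rests on.

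The cost is a sentence in Section 8.2.6, edits to those definition cells, a matching line in the data collection guideline, and a few extra fields abstracted from letters that researchers already open. No clinical procedure changes.
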